5.3.2. Safety Endpoints

Missing data for safety endpoints will not be imputed.

For dose groups, data collected after the dose escalation will not be included in the analyses. For regimen group, data from subjects with dose escalation back to tofacitinib 10 mg BID will be treated as it is.

5.3.3. Method of Handling the Data after Dose Escalation or Dose Reduction

For this study, subjects may have a dose escalation to 10 mg BID due to flare or dose reduction to 5 mg BID due to PE risk factors. The data after the dose change for the dose group and regimen group are handled as follows.

- For Tofacitinib 10 mg BID dose group: For subjects with dose reduction due to PE risk factor, data collected after the dose reduction will not be included in the safety and efficacy analyses, and last observation carried forward (LOCF) will be used for binary and continuous efficacy endpoints. The subjects will be considered as censored at the dose reduction time for endpoint of time to loss of remission (flare).
- For Tofacitinib 5 mg BID dose group: data collected after the dose escalation (with or without dose reduction due to PE risk factor after the dose escalation) from tofacitinib 5 mg BID to 10 mg BID will not be included in the safety and efficacy analyses. The subjects will be treated as non-responders for any visit after the dose escalation visit for binary efficacy endpoints. For continuous efficacy endpoints, the data collected for any visit after the dose escalation visit will be considered as missing. For time to loss of remission (flare), the subject will be considered as having an event at the visit with a dose escalation if the event criteria are met or having a censored time at the visit with a dose escalation if the event criteria are not met.
- For Tofacitinib 10 mg BID regimen group: For subjects with dose reduction due to PE risk factor, data collected after the dose reduction will be included in the safety and efficacy analyses.

- For Tofacitinib 5 mg BID regimen group: Data collected after the dose escalation will be included in the analyses. For subjects with dose reduction due to PE risk factor after the dose escalation, data collected after the dose reduction will be included in the safety and efficacy analyses.

The following table provides some examples on how to handle the data after the dose escalation for flare and dose reduction for risk factors for PE:

Table 2 Examples on How to Handle Data After Dose Change

Examples	Dose group		Regimen group	
	Safety analysis	Efficacy analysis	Safety analysis	Efficacy analysis
5 mg->10 mg at Month X	Data after Month X will not be included	Data after Month X will not be included. Subjects will be treated as non-responders after Month X for binary, and missing for continuous endpoints	Data after Month X will be included	Data after Month X will be included
10mg->5 mg at Month X	Data after Month X will not be included	Data after Month X will not be included. LOCF will be used	Data after Month X will be included	Data after Month X will be included.
5mg->10mg at Month X->5mg at Month Y	Data after Month X will not be included	Data after Month X will not be included. Subjects will be treated as non-responders after Month X for binary, and missing for continuous endpoints	Data after Month X(including data after Month Y) will be included	Data from Month X (including data after Month Y) will be included.

At the time of finalizing SAP V2, all subjects completed Month 6 and no subjects had dose reduction before Month 6. The data handling rules for dose reduction will not be applied for the primary analysis performed at Month 6, however they will be applied to the final analysis performed at the end of the study.

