7.2.3. Mayo Score

The Mayo score is an instrument designed to measure disease activity of UC. Mayo score ranges from 0 to 12 points. It consists of 4 subscores, each graded from 0 to 3 with higher scores indicating more severe disease (see [Appendix 2](#)).

- stool frequency (0-3).
- rectal bleeding (0-3).
- findings of flexible sigmoidoscopy (0-3).
- physician global assessment (PGA) (0-3).

Mayo score is assessed at Baseline, Month 6, Month 18, Month 30 and at Month 42/ET visits per the [Schedule of Activities](#).

The endoscopic findings will be locally read by study site investigator. The Mayo score will be calculated based on the subject's BM diary data (see [Section 7.2.1](#)) recorded over the 3 prior consecutive days.

The mucosal appearance of the sigmoidoscopic portion of endoscopic examination will be assessed for the Mayo endoscopic subscore, based on the definition provided in the protocol (see [Appendix 2](#)).

The PGA acknowledges the three other criteria, the patient's recollection of abdominal discomfort and general sense of wellbeing, and other observations, such as physical findings and the patient's performance status. The endoscopic subscore and the PGA should be

performed by a physician qualified to perform endoscopy, and it is recommended that the same physician performs all such assessments for a particular subject throughout the study, when possible.

Endpoints based on total Mayo score are defined below:

- Remission: total Mayo score of 2 points or lower, with no individual subscore exceeding 1 point and a rectal bleeding subscore of 0.
- Clinical response: decrease from baseline in total Mayo score of the Induction study, of at least 3 points and at least 30%, with an accompanying decrease in the subscore for rectal bleeding of at least 1 point, or absolute subscore for rectal bleeding of 0 or 1.
- Mucosal healing: an endoscopic subscore of 0 or 1.

Modified Mayo score consists of stool frequency subscore, rectal bleeding subscore and endoscopic subscore (ie, total Mayo score without PGA).

Endpoints based on modified Mayo score are defined below:

- Remission: an endoscopic subscore of 0 or 1, stool frequency subscore of 0 or 1, and rectal bleeding subscore of 0.

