5.2.1. Analyses for Binary Efficacy Data

The number and proportion of responders will be presented by dose group, regimen group and the subgroup of subjects who are initially assigned to tofacitinib 5 mg BID and later are retreated with tofacitinib 10 mg BID as described in [Section 5.2](#).

For dose comparison between tofacitinib 10 mg BID and 5 mg BID, the stratified estimation of the treatment difference between tofacitinib 10 mg BID and 5 mg BID in the proportion of subjects will be presented along with its 95% confidence interval (CI) with the endoscopic

subscore at baseline (0 versus 1) as the stratification factor. The Cochran Mantel Haenszel (CMH) weight method will be used for the stratified estimation of the treatment difference. The stratified CI will be constructed using the NewCombe method by Yan and Su (2010).¹ In addition, p-value based on CMH Chi-square test stratified by endoscopic subscore at baseline (0 versus 1) will be presented. The same analysis method will be used for regimen groups.

For the second secondary objective, in the subgroup of subjects who are initially assigned to tofacitinib 5 mg BID and later are retreated with tofacitinib 10 mg BID, the number and proportion of responders will be also presented overall and by the endoscopic subscore at baseline (0 versus 1).

As sensitivity analyses for handling of missing data, remission based on modified Mayo score and remission based on total Mayo score will also be analyzed using a generalized linear mixed-effects model with a logit link and with dose group, visit, dose group by visit interaction, endoscopic subscore at baseline (0 versus 1) all as fixed effects, and subject as a random effect based on data collected at Month 6, Month 18, Month 30 and Month 42 if sufficient data are available at Month 42. The estimated mean, mean difference, with p-values and 95% confidence interval based on the model will be presented at each time point for dose group and regimen group.

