5.3. Methods to Manage Missing Data

5.3.1. Efficacy Endpoints

For binary efficacy endpoints derived from total Mayo score or partial Mayo score, subjects with missing scores in an analysis window will be considered as non-responders.

For continuous endpoints that are measured repeatedly over time, the missing values will be handled in a linear mixed effects model where missing values are assumed to be missing at random.

For continuous endpoints based on total Mayo score and modified Mayo score, data collected after baseline to Month 6 will be considered as Month 6 if a subject has missing data at Month 6; data collected after Month 6 to Month 18 will be considered as Month 18 if a subject has missing data at Month 18; data collected after Month 18 to Month 30 will be considered as Month 30 if a subject has missing data at Month 30; data collected after Month 30 to Month 42 will be considered as Month 42 if a subject has missing data at Month 42. The description of the handling of missing data within individual components of the Mayo score is described in an [Appendix 2.1](#).

Subjects who drop out or complete the study without meeting the flare criteria will be censored at the last visit with Mayo score assessment for endpoint of time to loss of remission (flare).

Descriptive summary will also be presented based on observed data for efficacy data.

For the subgroup of subjects who are initially assigned to tofacitinib 5 mg BID and later are retreated with tofacitinib 10 mg BID, missing data will not be imputed.

For fecal calprotectin and hs-CRP, the missing values will be handled in a linear mixed effects model where missing values are assumed to be missing at random.

In addition, for hs-CRP, assayed values below the limit of quantification (BLQ) will be set to 10% less than the given assay lower limit for the specific biomarker. In listings BLQ values will be reported as “<LLQ” where LLQ will be replaced with the value for the lower limits of quantification. Assay values will be set to missing if a value has been collected as ND (ie, not done) or NS (ie, no sample).

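### Final dose-group analysis: LOCF after a risk-factor dose reduction has no time limit, so a 10 mg subject's Month 42 result can be a Mayo score 12 to 36 months old (minor)

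*SAP*

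**What the plan says.** SAP 5.3.3 covers subjects in the 10 mg dose group who move to 5 mg because of a risk factor. Their later data leave the dose-group analysis and "last observation carried forward (LOCF) will be used for binary and continuous efficacy endpoints". Table 2 repeats the rule for a 10 mg to 5 mg change at Month X: "Data after Month X will not be included. LOCF will be used". Neither place gives a longest carry or a last visit. Time to flare is handled differently, by censoring at the reduction.

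The scope is limited. After Table 2 the SAP says that "The data handling rules for dose reduction will not be applied for the primary analysis performed at Month 6", because no one had been reduced before Month 6. SAP 5.1 tests no formal hypotheses, although 5.2.1 presents confidence intervals and p-values.

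The neighbouring rules differ:
- Binary endpoints, SAP 5.3.1: "subjects with missing scores in an analysis window will be considered as non-responders".
- Continuous endpoints, SAP 5.3.1: missing values are left to a mixed model under missing at random. For total and modified Mayo scores, a score taken between two scheduled visits may first be assigned to the later one if that one is missing.
- Escalated 5 mg subjects, SAP 5.3.3: non-responders on binary endpoints, and "For continuous efficacy endpoints, the data collected for any visit after the dose escalation visit will be considered as missing".

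Protocol 7.2.3 sets the timing: "Mayo score is assessed at Baseline, Month 6, Month 18, Month 30 and at Month 42/ET visits".

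**The concern.** Taking post-reduction data out of the dose-group analysis fits the primary objective, which compares subjects who stay on 10 mg. The difficulty is what is put in their place. Carrying a score forward assumes that disease activity froze at the last assessment. For endpoints that need endoscopy, that assessment may be up to 12 months old at the reduction and 36 months old by Month 42. Partial Mayo endpoints and biomarkers are measured at most visits, so they start from a fresher value, but their carry is just as open-ended.

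Subjects enter in stable remission (Protocol 4.1), so carried values are probably mostly remissions. If remission declines over time, the 10 mg proportions at Months 18 to 42 are then too high. Amendment 1 lengthened the study partly to watch for divergence of efficacy between the dose groups, and these are the visits affected.

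Two things are also left unsaid. The SAP does not state whether LOCF continues after a reduced subject leaves the study. Nor does it state whether carried values enter the sensitivity model of 5.2.1.

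**Working it through.** **Yardstick.** Protocol 9.1 gives a half width of about 16% for the Month 6 difference, with 65 per group and rates above 70%. Check: 1.96 × √(2 × 0.7 × 0.3 / 65) = 15.8 points. The figure reproduces.

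**Length of carry to Month 42.** From Month 6: 42 − 6 = 36 months. From Month 18: 24. From Month 30: 12. A reduction between Months 6 and 18 fills Months 18, 30 and 42 with the Month 6 result.

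**Inputs not in the documents (assumed).** Share of the 10 mg group reduced, q = 5-10%. Annual permanent loss of remission on 10 mg, a = 12-20%. Reductions spread evenly over Months 12-36, or early, over Months 6-23.

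**Formula.** S(t) = (1 − a)^(t/12) is the proportion in remission at month t. Overstatement at Month 42 = q × (E[S(L)] − S(42)), where L is the month of the carried score.
- Months 12-36: 25% carry Month 6, 50% Month 18, 25% Month 30.
- Months 6-23: 12/17 = 71% carry Month 6, 5/17 = 29% Month 18.

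**Worked case.** a = 12%, q = 10%, Months 12-36. S(6) = 0.938, S(18) = 0.826, S(30) = 0.727, S(42) = 0.639. E[S(L)] = 0.25 × 0.938 + 0.5 × 0.826 + 0.25 × 0.727 = 0.829. Overstatement = 10% × (0.829 − 0.639) = 1.9 points.

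**Results for q = 10%, in percentage points (halve for q = 5%).** Each cell shows a = 12 / 16 / 20%.

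| Assumption | Months 12-36 | Months 6-23 |
|---|---|---|
| Only scheduled scores carried | 1.90 / 2.33 / 2.67 | 2.66 / 3.30 / 3.84 |
| Losses before reduction caught by symptom-driven endoscopy, so S at the reduction time is carried | 1.37 / 1.66 / 1.87 | 2.19 / 2.69 / 3.09 |
| Scheduled scores, half of lost remissions regained per year | 0.45 / 0.56 / 0.66 | 0.77 / 0.98 / 1.17 |

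Over q = 5-10% and both timings the ranges are 0.9-3.8, 0.7-3.1 and 0.2-1.2 points. If remission is 70% at Month 6 with the same decline, the first row becomes 1.41 / 1.78 / 2.09 and 1.98 / 2.52 / 3.00.

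**Outer case.** The only retention figure is 72.7% at 12 months on 5 mg, from the open-label study (Protocol 1.2). Applied as a 27.3% annual loss over 42 months with q = 10%, scheduled scores give 3.1 and 4.6 points. That stretches a 12-month figure on the other dose, so it bounds the range rather than estimates it.

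**The case against.** **The plan already shows most of the effect.** As SAP 5.2 defines them, the 10 mg dose group and the 10 mg regimen group are the same randomised subjects. Under 5.3.3 they are handled differently only after a reduction. Both sets of proportions are planned for the final analysis, so setting the two 10 mg rows side by side shows what LOCF changed for every binary endpoint. This stands, and it is the main reason for the low grade. What is missing is a contrast with a confidence interval: the planned regimen comparison also brings in post-escalation 5 mg data.

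**The arms are not treated unequally in the way that a reader might infer.** Escalation follows a confirmed flare (Protocol 5.11), so non-response records a treatment failure. A reduction follows a safety risk factor, and scoring it as non-response would penalise 10 mg for something other than efficacy. A never-escalated 5 mg subject moved to open-label 5 mg keeps the same dose, so there is nothing to replace. This stands for binary endpoints. It does not explain why the continuous endpoints need LOCF when the mixed model is available.

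**A reader might infer that LOCF keeps later dropouts as responders.** The SAP does not say so, and the non-responder rule of 5.3.1 could equally apply. The gap is real, but that reading is not established.

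**The sensitivity model helps only in part.** The SAP says that "remission based on modified Mayo score and remission based on total Mayo score will also be analyzed using a generalized linear mixed-effects model", "based on data collected at Month 6, Month 18, Month 30 and Month 42 if sufficient data are available at Month 42". The reference to collected data suggests that carried values stay out, without saying so. Mucosal healing and clinical response are not named.

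**Conclusion.** The point holds as a minor one. The rule has no time limit. For continuous endpoints it departs from the SAP's own mixed-model approach. Its bias at Months 18 to 42 probably favours 10 mg.

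The size rests on assumed reduction shares, timings and loss rates. Under them it is about 0.2 to 3.8 points at Month 42, well below the 16-point half width. The bias shrinks if remission is regained, and a carried non-remission pulls the other way.

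The documents do not support three stronger conclusions. The Month 6 primary result is not affected, because the SAP exempts it. The rule is not hidden, because the 10 mg regimen row uses the post-reduction data. A new main method for binary endpoints is not required: 5-10% of about 69 subjects (138 enrolled at Amendment 2, allocated 1:1) is roughly 3 to 7 people, in a secondary analysis without formal hypotheses.

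**What to change.** Amend the SAP before the final database lock:

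1. **Continuous endpoints.** Set post-reduction visits to missing and use the planned mixed model, as for escalated 5 mg subjects. State whether the between-visit reassignment of 5.3.1 still applies to scores taken before the reduction.
2. **Binary endpoints.** Keep the prespecified LOCF analysis. Add a named sensitivity contrast: 10 mg subjects as observed after reduction (the regimen-group row) against the 5 mg dose group, with missing counted as non-response. Report the CMH-weighted difference with its Newcombe 95% interval.
3. **End of the carry.** State that LOCF stops when the subject leaves the study, after which the non-responder rule of 5.3.1 applies.
4. **Sensitivity model, SAP 5.2.1.** State that LOCF values do not enter it, and add mucosal healing and clinical response.

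Multiple imputation of the binary endpoints is optional.

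The cost is SAP wording and a little programming, with no new data. There are two downsides. SAP 7.1 has the sponsor's study team unblinded from the Month 6 analysis onward, so the amendment should be documented as made after unblinding, with the LOCF results reported alongside. The contrast in item 2 uses outcomes observed on 5 mg after the reduction, so it tests the LOCF result but does not estimate what continued 10 mg would have given.

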Once the subject is confirmed to meet the definition for flare, documented by site read endoscopy, the investigator may adjust the dose through the IRT system provided that the subject does not have any of the risk factors for venous thromboembolism (see [Section 7.3.6](#)). Once confirmed by the investigator, subjects may have a dose increase to 10 mg BID or remain on 10 mg BID, depending on their initial treatment assignment. Dose adjustments for confirmed flare will not be permitted prior to the Month 1 study visit.

Subjects who develop one or more of the risk factors for venous thromboembolism during the study will not be permitted to increase their tofacitinib dose to 10 mg BID should they experience a flare of their UC.

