2.1. Study Objectives

Primary Objective

- To evaluate the efficacy and safety of tofacitinib in subjects in stable remission on 10 mg BID who decrease the dose to and remain on 5 mg BID (“5 mg BID dose group”) compared to subjects remaining on 10 mg BID.

Secondary Objectives

- To evaluate the efficacy and safety of tofacitinib in subjects in stable remission on 10 mg BID who decrease the dose to 5 mg BID with option for dose escalation for flare (“flexible dosing regimen”) compared to subjects staying on 10 mg BID.
- To evaluate the efficacy and safety of the subset of subjects in stable remission on 10 mg BID who have flare after dose decrease to tofacitinib 5 mg BID and are re-treated with 10 mg BID.

[figure not shown]

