5.2.2. Analyses for Continuous Efficacy Data

The descriptive statistics will be used to summarize continuous data. The continuous data and change from baseline will be summarized descriptively by visit and dose group, regimen group and the subgroup of subjects who are initially assigned to tofacitinib 5 mg BID and later are retreated with tofacitinib 10 mg BID.

For continuous efficacy endpoints based on total Mayo score evaluated for primary objective at Month 6, the change from baseline will be analyzed using an analysis of covariance (ANCOVA) model with dose group, the endoscopic subscore at baseline (0 versus 1) as factors and baseline score as a covariate. Otherwise, for continuous efficacy endpoints, the change from baseline will be analyzed using linear mixed effects model with baseline value, dose group or regimen group, the endoscopic subscore at baseline (0 versus 1), visit, and dose group or regimen group by visit interaction all as fixed effects, and subject as a random effect. The adjusted estimations and associated 95% CI for the overall difference between the two dose groups or two regimen groups will be computed at each visit.

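### Partial Mayo change scores, dose-group comparison: 5 mg values after flare escalation become missing at random while 10 mg post-flare values stay, so the model does not estimate the course on continued 5 mg

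*SAP*

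**What the plan says.** The primary objective, which the dose-group comparison serves, concerns subjects "who decrease the dose to and remain on 5 mg BID" (SAP 2.1).

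- **5 mg dose group.** SAP 5.3.3: "For continuous efficacy endpoints, the data collected for any visit after the dose escalation visit will be considered as missing". Protocol 9.2.3 has the same rule. The score at the escalation visit itself is kept.
- **10 mg dose group.** The only exclusion in SAP 5.3.3 is for dose reduction because of embolism risk factors: "data collected after the dose reduction will not be included in the safety and efficacy analyses". Nothing removes values after a flare. Under Protocol 5.11, after a confirmed flare "subjects may have a dose increase to 10 mg BID or remain on 10 mg BID, depending on their initial treatment assignment".
- **Missing values.** SAP 5.3.1: they are "handled in a linear mixed effects model where missing values are assumed to be missing at random".
- **Model.** SAP 5.2.2 lists baseline, group, endoscopic stratum, visit and "dose group or regimen group by visit interaction all as fixed effects, and subject as a random effect". The current text names no other within-subject structure.
- **Total and modified Mayo.** SAP 5.3.1 moves a score obtained since the previous endoscopy visit to Month 6, 18, 30 or 42 when that visit is missing. SAP 5.2.2 analyses total Mayo at Month 6 by ANCOVA.
- **Sensitivity analysis.** The only missing-data sensitivity analysis named (SAP 5.2.1) is for binary remission.

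**The concern.** The same event, a confirmed flare, is handled differently by arm. A 5 mg subject who escalates contributes one flare score and is then treated as if the rest were ignorable. A 10 mg subject who flares and stays contributes the post-flare scores as well. The model must therefore supply the post-flare course on 5 mg from mainly pre-flare data. For binary endpoints the same SAP counts escalation as failure.

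At stake is how the continuous secondary results are read. They could suggest maintained efficacy on 5 mg while remission and time to flare show a loss. With quick recovery they could instead exaggerate late harm. Protocol Amendment 1 gave possible divergence between the dose groups as one reason for extending follow-up to 42 months, and later visits are where more subjects have escalated.

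**Working it through.** **The plan's own figure.** There is none for these endpoints. The stated half-width of about 16% concerns the binary primary endpoint and reproduces: 1.96 × √(2 × 0.7 × 0.3 / 65) = 15.8%.

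**Step 1: what a random subject effect predicts after a flare.** For n post-baseline visits, the predicted subject deviation is [nτ² / (nτ² + σ²)] × mean residual. Assume τ = 0.4, σ = 0.6, visits at Months 1, 3 and 6 at the arm mean, and a flare of +3.5 at Month 9.
- Mean residual: 3.5 / 4 = 0.875.
- Factor: 4 × 0.16 / (4 × 0.16 + 0.36) = 0.64.
- Prediction: 0.64 × 0.875 = 0.56 points above the arm mean.

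The factor is below 1 for any variances, so the prediction stays below 0.875. With 10% recovery per visit, the expected excess at the next visit is 0.9 × 3.5 = 3.15. The model therefore assumes near-recovery.

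**Step 2: inputs for a trial-level check.**
- 5 mg flare rate: Protocol 1.2 reports 72.7% still in remission after 12 months on 5 mg. As a proxy with constant hazard this is 1 − √0.727 = 14.7% per 6 months.
- 10 mg flare rate: not given; assumed 5% or 8% per 6 months.
- Flare size +3.5 and recovery of 10% to 50% per visit, equal in both arms: assumed.
- Escalation and withdrawal: either all 5 mg flarers escalate and nobody withdraws, or 85% escalate and non-escalated subjects still in flare withdraw at 20% per visit (assumed).

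**Step 3: true difference at Month 18, 10% recovery.** Difference = 3.5 × [P5 − P10], where P is the share still in flare: the sum over visits of P(flare in that interval) × 0.9^(later visits).
- 5 mg intervals to Months 1, 3, 6, 9, 12, 15, 18: 0.026, 0.050, 0.071, 0.065, 0.060, 0.056, 0.051. The weights run from 0.9⁶ to 1, so P5 = 0.288.
- In the same way, P10 = 0.110 (5% rate) or 0.170 (8% rate).
- Differences: 3.5 × 0.178 = 0.62 and 3.5 × 0.118 = 0.41.

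The simulated true values below differ from these by up to about 0.05, which shows the simulation error.

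**Step 4: planned model against truth, partial-type score, Month 18 (5 mg minus 10 mg; positive means 5 mg is worse).**

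| Recovery per visit | 10 mg rate | Escalation | Model | True | Share lost |
|---|---|---|---|---|---|
| 10% | 5% | all, no withdrawal | 0.06 | 0.57 | 89% |
| 10% | 8% | all, no withdrawal | −0.08 | 0.45 | 118% |
| 10% | 5% | 85%, withdrawal | 0.26 | 0.63 | 59% |
| 10% | 8% | 85%, withdrawal | 0.02 | 0.37 | 95% |
| 20% | 5% | all, no withdrawal | 0.15 | 0.45 | 67% |
| 20% | 8% | all, no withdrawal | −0.03 | 0.30 | 110% |
| 20% | 5% | 85%, withdrawal | 0.30 | 0.48 | 38% |
| 20% | 8% | 85%, withdrawal | 0.11 | 0.35 | 69% |

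Share lost = 1 − model / true. At Month 6 the loss was understated in all 16 settings (recovery 10% to 50%), by about 18% to 61%. With 50% recovery the sign of the bias changes at late visits: at Month 42 the model gave 0.46 against a true 0.11.

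**Step 5: total and modified Mayo** (flare +3, 10 mg rate 8%, flares persist, nobody withdraws). With the SAP 5.3.1 fill applied to escalated subjects, Month 6 is preserved (0.18 v 0.18) and Month 42 is attenuated (0.14 v 0.71). If half of flares resolve, the average over visits is biased against 5 mg (0.59 v 0.24). If the fill is not applied, the average is −0.61 v 0.47. The SAP does not say whether the fill covers visits that SAP 5.3.3 sets to missing.

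**The case against.** A reader might infer that the plan erases or reverses a true loss on 5 mg for every continuous Mayo endpoint. The documents do not support that.
- For total and modified Mayo, the fill, if it applies, carries the flare score to the next endoscopy visit, and total Mayo at Month 6 does not use the mixed model.
- Escalation is optional, is barred before Month 1, and is barred with thromboembolism risk factors. Some 5 mg flarers may therefore have post-flare data in the analysis.
- Rescue therapy or surgery for UC means withdrawal (Protocol 5.10, 6.4), so 10 mg flarers do not all contribute every later score.

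These points stand. They reduce the bias for partial scores but do not remove it, as the 85% rows show. Harsher runs, with every 5 mg flarer escalating and flares that mostly persist, give a clear reversal (average −0.47 v 0.45 at an 8% rate) or erasure even at 5% (−0.02 v 0.48). They show how far the result can move and are not a forecast.

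A reader might also infer that the trial's main result is affected. It is not: escalators count as non-responders in the binary analyses. No formal hypotheses are tested, and time to flare and binary partial Mayo remission will be reported alongside. That limits the consequence. The observed-data summaries offer no check, because for the dose groups they carry the same one-sided exclusion. The regimen comparison includes re-treatment data and answers a different question.

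**Conclusion.** The concern holds for the dose-group comparison of partial and modified partial Mayo change. The asymmetry is in the text, although its 10 mg half rests on the absence of a rule rather than on a statement. The model does not target the course on continued 5 mg, and no inferential check is planned.

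Under slow recovery (10-20% per visit), about a third to nearly all of the loss on 5 mg disappears at Months 6 to 18 in most settings. Within that range, erasure or slight reversal needs nearly all 5 mg flarers to escalate and a fairly high 10 mg flare rate. Under fast recovery, late visits overstate harm on 5 mg. For total and modified Mayo, Month 6 is protected if the fill applies, and later visits can be biased either way.

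All sizes rest on assumed 10 mg flare rates, flare size, recovery, escalation and withdrawal, and on the same post-flare course in both arms. These are secondary endpoints, so the change should be made but does not threaten the primary analysis.

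**What to change.** In SAP 5.2.2 and 5.3.3, for the repeated continuous Mayo endpoints in the dose-group comparison:

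1. Add one inferential sensitivity analysis. Multiply impute each escalated 5 mg subject's post-escalation visits from the post-flare visits of subjects who flared and were not escalated (mainly 10 mg), matched on time since flare. Then fit the planned model.
2. Report the flare score carried forward in both dose groups as a pessimistic bound, not as a replacement estimate. For partial Mayo at an 8% rate on 10 mg it matched the truth when flares persisted (0.43 v 0.43) but overstated the loss when half resolved (0.44 v 0.20).
3. State that the SAP 5.3.1 fill applies to visits that SAP 5.3.3 sets to missing.
4. State that the missing-at-random result alone will not be read as maintained efficacy on 5 mg if these analyses change the direction of the difference or whether its 95% CI excludes zero.

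Setting post-flare values to missing in both arms is not enough: it kept the sign but recovered only 0.09 of a true 0.44 for partial Mayo.

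The cost is SAP wording and extra model runs on data already collected. The donor pool is small: with 138 / 2 = 69 per arm, 69 × (1 − 0.95³) ≈ 10 to 69 × (1 − 0.92³) ≈ 15 subjects on 10 mg would have flared by Month 18, before withdrawals, so the interval will be wider. The imputation also assumes that the post-flare course on 5 mg is no worse than on 10 mg. This cannot be tested, and if it is wrong the result still flatters 5 mg. In simulation the imputation came close to the truth (0.32 v 0.34 at Month 6, 0.63 v 0.58 at Month 18), but that simulation built in the same assumption.
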